11.5 Disclosure of Data

Data generated by this study must be available for inspection by the FDA, the Sponsor or their designee, applicable foreign health authorities, and the IRB as appropriate. Subjects may request their medical information be given to their personal physician or other appropriate medical personnel responsible for their welfare.

Subject medical information obtained during the study is confidential and disclosure to third parties other than those noted above is prohibited.

11.6 Retention of Records

To enable evaluations and/or audits from and permit access for regulatory authorities or the Sponsor, the Investigator will keep records, including the identity of all participating subjects (sufficient information to link records, eg, eCRFs and hospital records), all original signed ICFs, copies of all eCRFs, SAE forms, source documents, and detailed records of treatment disposition. The records should be retained by the Investigator according to specifications in the ICH guidelines, local regulations, or as specified in the Clinical Study Agreement, whichever is longer. The Investigator must obtain written permission from the Sponsor before disposing of any records, even if retention requirements have been met.

If the Investigator relocates, retires, or for any reason withdraws from the study, the Sponsor should be prospectively notified. The study records must be transferred to an acceptable designee, such as another Investigator, another institution, or to the Sponsor.

11.7 Publication Policy

Following completion of the study, the data may be considered for publication in a scientific journal or for reporting at a scientific meeting. Each Investigator is obligated to keep data pertaining to the study confidential. The Investigator must consult with the Sponsor before any study data are submitted for publication. The Sponsor reserves the right to deny publication rights until mutual agreement on the content, format, interpretation of data in the manuscript, and journal selected for publication are achieved.

11.8 Financial Disclosure

Investigators are required to provide financial disclosure information to the Sponsor to permit the Sponsor to fulfill its obligations under 21 CFR Part 54. In addition, Investigators must commit to promptly updating this information if any relevant changes occur during the study and for a period of 1 year after the completion of the study.

12 STUDY ADMINISTRATIVE INFORMATION

12.1 Protocol Amendments

Any amendments to the study protocol will be communicated to the Investigators by Medpace or the Sponsor. All protocol amendments will undergo the same review and approval process as the original protocol. A protocol amendment may be implemented after it has been approved by the IRB, unless immediate implementation of the change is necessary for subject safety. In this case, the situation must be documented and reported to the IRB within 5 working days.

APPENDIX A: SCHEDULE OF PROCEDURES

Day (± Visit Window)	Screening ^a See Footnote ^a	Treatment Period							Post-Treatment Observation Period ^b			Unscheduled Visit ^b
		1	2	3	4	5	6	7 ^c	14 (±2 d)	21 (±2 d)	28 (±3 d)	
Informed consent ^d	X											
Eligibility criteria	X											
Demographic information	X											
Medical history	X											
Prior/concomitant medications	X	X	X	X	X	X	X	X	X	X	X	X
Urine pregnancy test ^{e,f}	X											
Blood chemistry, hematology, and coagulation ^{f,g}	X	X		X		X		X	X	X	X	X
SARS-CoV-2 test ^{f,h}	X											
Blood sampling for PK ⁱ		X					X					
12-lead electrocardiogram ^j	X							X				
Temperature	X											
Vital signs ^k	X	X	X	X	X	X	X	X	X	X	X	X
Pulse oximeter for SpO ₂ :FiO ₂ or ABG ^{f,l} for PaO ₂ :FiO ₂ ^m	X	X	X	X	X	X	X	X	X	X	X	X
Clinical status ⁿ	X	X	X	X	X	X	X	X	X	X	X	X
Blood sampling for CRP and D-dimer biomarkers ^{f,o}	X							X				X
Blood sampling for vascular leakage and inflammation biomarker ^{s,p,o}	X							X				X
Randomization ^q		X										
Study drug administration ^r		X	X	X	X	X	X	X				
Adverse events		X	X	X	X	X	X	X	X	X	X	X

Note: This Schedule of Procedures does not include assessments that are part of standard of care.

- Unless otherwise specified, all Screening assessments must be performed within 24 hours prior to randomization. The Screening and Day 1 procedures may be performed on the same calendar day. Study Days may not correspond exactly with calendar days.
- During the Post-Treatment Observation Period, the site will perform weekly telephone visits for subjects who have been discharged to assess concomitant medications, clinical status, and adverse events. If a subject reports a decline in clinical status at a telephone visit, then per the discretion of the Investigator, the subject will be requested to return to the site for an Unscheduled Visit. For subjects who remain in the hospital during the Post-Treatment Observation Period, assessments will be performed at the site as indicated.
- For subjects who are discharged prior to Day 7, all of the Day 7 procedures will be performed on the day of discharge. For subjects who are discharged on Days 1 through 4, concomitant medications, clinical status, and adverse events will be assessed by a telephone visit on Day 7 (±2 d). If a subject discontinues from study drug prematurely, site

staff should make every effort to complete the full panel of assessments scheduled for the Day 7 visit (except study drug administration). Subjects who discontinue study drug should continue to complete all safety assessments at subsequent study visits up to and including Day 28, unless the subject or LAR withdraws consent or is lost to follow-up. The reason for subject discontinuation from study drug or study withdrawal must be documented in the source and eCRFs.

- d. Signed informed consent must be obtained before any study-related procedures are performed.
- e. For females of childbearing potential only.
- f. Assessment will be performed at the local laboratory.
- g. If a blood chemistry, hematology, or coagulation assessment was performed within 24 hours prior to the first dose of study drug, it is not necessary to repeat the assessment on Day 1. Effort should be made to obtain blood chemistry, hematology, and coagulation at approximately the same time on each day indicated; however, it should not be considered a protocol deviation if this is not possible. After the Treatment Period, blood chemistry, hematology, and coagulation will be assessed weekly until Day 28, unless discharged.
- h. Laboratory-confirmed active SARS-CoV-2 infection must be determined by PCR or other commercial or public health assay in any specimen, as documented by either of the following: SARS-CoV-2 PCR positive in sample collected <72 hours prior to randomization; OR SARS-CoV-2 PCR positive in sample collected \geq 72 hours prior to randomization, documented inability to obtain a repeat sample (eg, due to lack of testing supplies, limited testing capacity, results taking >24 hours to obtain, etc), AND progressive disease suggestive of ongoing SARS-CoV-2 infection.
- i. Blood samples for PK analysis will be collected on Day 1 and Day 6 at 30 (\pm 15) minutes and 90 (\pm 15) minutes after the first study drug dose of the day. The exact time of study drug administration and the exact time of blood sample for PK analysis collection will be recorded on the eCRF. PK analysis will be performed at a central laboratory. Blood samples for PK analysis will be collected for all subjects; however, samples for subjects randomized to placebo will not be analyzed. Blood samples for PK analysis will be collected for all subjects in Part 1; blood samples for PK analysis may be collected for subjects in Part 2, after review of the PK data in Part 1.
- j. If a 12-lead electrocardiogram was performed within 24 hours prior to informed consent, it is not necessary to repeat the 12-lead electrocardiogram at Screening.
- k. Vital signs will include blood pressure, heart rate, SpO₂ (for non-ventilated subjects only), and respiratory rate. If vital signs are to be assessed at the same time point as a blood draw, vital signs should be assessed prior to blood draw. Vital signs will be assessed within 1 hour prior to each dose of study drug and 30 (\pm 15) minutes, 60 (\pm 15) minutes, and 90 (\pm 15) minutes following each dose of study drug. Additionally, after the first dose of study drug, supine blood pressure will be assessed every 5 (\pm 1) minutes for the first 15 minutes, and then every 15 (\pm 5) minutes for the first hour. Subjects will be in the supine position during dosing, and they must remain supine with their head no higher than 45° until the vital sign assessment is completed 90 minutes following dosing. After the Treatment Period, vital signs will be assessed daily until Day 28, unless discharged.
- l. ABG should be obtained only if clinically indicated. If ABG is obtained, the subject's current oxygen requirement should also be recorded.
- m. During the Treatment Period, SpO₂:FiO₂ or PaO₂:FiO₂ (if ABG is being performed per standard of care) will be assessed TID, within 1 hour prior to each dose of study drug. After the Treatment Period, SpO₂:FiO₂ or PaO₂:FiO₂ (if ABG is being performed per standard of care) will be assessed daily until Day 28, unless discharged.
- n. During the Treatment Period, clinical status will be assessed TID, within 1 hour prior to each dose of study drug, using the NIAID 8-point ordinal scale. After the Treatment Period, clinical status will be assessed once daily until Day 28, unless discharged. If the subject is discharged alive prior to Day 28, clinical status will be assessed at the Post-Treatment Observation Period telephone visits only.
- o. For all subjects remaining hospitalized on Day 14 or beyond, blood sampling for biomarkers will also occur on Day 28 or the day of hospital discharge, whichever occurs first.
- p. Vascular leakage and inflammation biomarker (Angpt-2, IL-6, IL-8, TNF α , and HMGB-1) analysis will be performed at a central laboratory.
- q. After it is determined that all eligibility criteria have been met, the subject will be randomized.
- r. A volume of 0.50 mL or 0.75 mL of study drug will be administered TID (Q8H) by SC injection to the abdomen. Subjects will be dosed for 7 days (21 doses) or until discharge from the hospital (or death), whichever occurs first. Subjects will be in the supine position during dosing, and they must remain supine with their head no higher than 45° until the vital sign assessment is completed 90 minutes following dosing. The first study drug administration must occur within 12 hours after randomization. Study drug should be administered at the same nominal times (\pm 1 hour) for each Q8H dose throughout the Treatment Period. Prior to the initiation of Part 2, the DRC may make a recommendation to increase the study drug dosing duration to up to 14 days. If the study drug dosing duration is increased, the Day 5 procedures will be performed on Day 8 through the day before the last day of dosing, and the Day 7 procedures will be performed on the last day of dosing.

Abbreviations: ABG = arterial blood gas; Angpt = angiopoietin; CRP = C-reactive protein; d = days; DRC = Data Review Committee; eCRF = electronic case report form; FiO₂ = fractional inspired oxygen; HMGB-1 = high mobility group box 1; IL = interleukin; NIAID = National Institute of Allergy and Infectious Diseases; PaO₂ = partial pressure of oxygen; PCR = polymerase chain reaction; PK = pharmacokinetic(s); Q8H = every 8 hours; SARS-CoV-2 = severe acute respiratory syndrome coronavirus 2; SC = subcutaneous; SpO₂ = peripheral capillary oxygen saturation; TID = three times daily; TNF α = tumor necrosis factor alpha.

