3 STATISTICAL METHODOLOGY

3.1 General Considerations

3.1.1 *Analysis Day*

Analysis day will be calculated from the date of first dose of study drug. The day of the first dose of study drug will be Day 1, and the day immediately before Day 1 will be Day -1. There will be no Day 0.

3.1.2 *Definition of Baseline*

Baseline is defined as the last measurement prior to the first dose of study drug.

3.1.3 *Visit Windows*

No analysis visit windows will be defined for this study, i.e., the nominal visits /time-points will be used for all statistical summaries/analyses.

3.1.4 *Summary Statistics*

Categorical data will generally be summarized with counts and percentages of subjects. The denominator used for the percentage calculation will be clearly defined. Continuous data will generally be summarized with descriptive statistics including n (number of non-missing values), mean, median, standard deviation, minimum, and maximum.

Summaries of change from baseline variables will include only patients who have both a baseline value and corresponding value at the post-baseline time point of interest.

3.1.5 *Hypothesis Testing*

All statistical comparisons will be made using two-sided tests at $\alpha = 0.05$. All null hypotheses will be of no treatment difference, and all alternative hypotheses will be two-sided. Confidence intervals will be two-sided, unless stated otherwise.

3.1.6 *Handling of Dropouts and Missing Data*

For all efficacy endpoints that do not include death as a possible outcome, data from subjects who die prior to Day 28 will be imputed at Day 28 based on the worst outcome. Other missing data for selected endpoints will be imputed using the methods as described in Section 3.4.

In cases of missing or incomplete dates (e.g. AE and concomitant medications), the missing component(s) will be assumed as the most conservative value possible. For example, AEs with missing start dates, but with stop dates either overlapping into the treatment period or missing,

will be counted as treatment-emergent, taking the worst-case approach. When partial dates are present in the data, both a partial start date and/or a partial stop date will be evaluated to determine whether it can be conclusively established that the AE started prior to the start of study drug or ended prior to the start of study drug. If the above cannot be conclusively established based on the partial and/or present dates, then the AE will be considered as treatment-emergent.

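### For subjects discharged on Days 5–6, the only scheduled NIAID grade near Day 7 comes from the day of discharge, and no rule prevents an inpatient grade from standing as their Day 7 status

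*Protocol*

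**What the plan says.** Four provisions bear on the Day 7 NIAID value.

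- **Protocol Appendix A, footnote c.** "For subjects who are discharged prior to Day 7, all of the Day 7 procedures will be performed on the day of discharge". Clinical status is one of the Day 7 procedures. The footnote then adds a telephone check of clinical status on Day 7, within 2 days either side, but only for subjects discharged on Days 1 through 4.
- **Protocol Appendix A, footnote n.** For inpatients, "During the Treatment Period, clinical status will be assessed TID, within 1 hour prior to each dose of study drug". After that, "If the subject is discharged alive prior to Day 28, clinical status will be assessed at the Post-Treatment Observation Period telephone visits only". The first of those calls in the schedule is Day 14.
- **SAP section 3.1.3.** "No analysis visit windows will be defined for this study, i.e., the nominal visits /time-points will be used for all statistical summaries/analyses".
- **Protocol section 7.2.** Grades 2 to 6 all describe a hospitalized subject. Grades 7 and 8 describe a subject who is not hospitalized.

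Two SAP endpoints use the Day 7 grade directly: the proportion improving by at least 2 categories from baseline to Day 7 (CMH test, section 3.4.1) and the number of subjects in each category at Day 7 (descriptive). The SAP allows a discharge value in place of Day 7 for the PaO2:FiO2 endpoint. It has no such wording for the NIAID endpoints.

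**The concern.** The NIAID endpoints are defined at Day 7, but for Day 5–6 discharges the schedule obtains no status on or after the day they leave other than the discharge-day record. If that record is an inpatient grade and is carried under the nominal Day 7 label, a subject known to be at home on Day 7 is counted as hospitalized and may be counted as not improved. The same subject could be a success on another listed endpoint, discharge free of respiratory failure before Day 7.

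A related gap affects subjects discharged on Days 1–4. They may have two Day 7 records, one from the discharge day and one from the call, and the SAP does not say which counts. Footnote n, read literally, also leaves no room for the call that footnote c requires.

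At stake is a Day 7 improvement rate that is too low. If the drug brings discharge forward, as the Protocol's study rationale expects by predicting earlier recovery, the Day 7 treatment difference would be too small as well.

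**Working it through.** The documents give no power, effect size, discharge rate or baseline grade mix, so there is no planned figure to reproduce. The check has three steps.

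**1. Which Day 7 records exist (Appendix A, footnotes c and n)**

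| Discharge | Discharge-day status | Day 7 call | Next scheduled status |
|---|---|---|---|
| Days 1–4 | yes | yes (footnote c) | Day 14 call |
| Days 5–6 | yes | no | Day 14 call |
| Still inpatient on Day 7 | not applicable | not applicable | Day 7 itself |

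**2. What an inpatient grade does to the improvement endpoint**

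Improvement requires recorded grade minus baseline grade ≥ 2. An inpatient can be graded 6 at most.

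| Baseline | Grade needed | Reachable as inpatient | Met at grade 7 |
|---|---|---|---|
| 3 | 5 | yes, at 5 or 6 | yes |
| 4 | 6 | only at 6 | yes |
| 5 | 7 | no | yes |
| 6 | 8 | no | only at 8 |

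Baseline 5 is therefore always affected by an inpatient grade. Baseline 4 is affected if recorded as 4 or 5, and baseline 3 only if recorded as 3 or 4. Baseline 5 is foreseeable: moderate disease can qualify with SpO2 above 93% on room air, and moderate subjects may be about half of enrolment (Protocol section 4.1). The category table at Day 7 is wrong for every baseline grade, because the subject is placed in 6 or below instead of 7 or 8.

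**3. Size, on assumed rates**

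Assumptions: 15–25% of subjects are discharged on Days 5–6; of these, 30–45% had baseline grade 5 and 50% had baseline grade 4; all are at home on Day 7.

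Undercount of improvers = share discharged on Days 5–6 × share of those mis-scored.

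- Discharge day graded 7 or 8: 0 points.
- Only baseline 5 mis-scored: 0.15 × 0.30 = 4.5 points, to 0.25 × 0.45 = 11.25 points.
- Baseline 5 and half of baseline 4 mis-scored: the share is 0.30 + 0.25 = 0.55, to 0.45 + 0.25 = 0.70. The undercount is 0.15 × 0.55 = 8.25 points, to 0.25 × 0.70 = 17.5 points.

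Loss in the treatment difference = (active share − placebo share discharged on Days 5–6) × share mis-scored. With 25% against 15% this is 0.10 × 0.30 to 0.10 × 0.45 = 3 to 4.5 points, or 0.10 × 0.55 to 0.10 × 0.70 = 5.5 to 7 points.

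A separate illustration of power uses assumed true improvement rates of 45% and 65%, two-sided alpha 0.05 (SAP section 3.1.5), and about 120 subjects in Part 2, giving 40 per arm at 1:1:1 or 80:40 at 2:1. Power = Φ[(difference − 1.96 × SE0)/SE1], with SE0 pooled and SE1 unpooled.

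| Scenario | Rates | Difference | Power, 40 per arm | Power, 80:40 |
|---|---|---|---|---|
| No mis-scoring | 45% v 65% | 20 points | 43% | 55% |
| 20% leave on Days 5–6 in both arms, half mis-scored | 35% v 55% | 20 points | 43% | 54% |
| 15% v 30% leave on Days 5–6, half mis-scored | 37.5% v 50% | 12.5 points | 20% | 25% |

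Equal discharge timing lowers both rates and leaves the difference intact. Earlier discharge on drug shrinks it.

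**The case against.** The strongest reply is that this is an undefined value, not a documented scoring error. SAP section 3.1.3 does not say in terms that a discharge-day grade becomes the Day 7 NIAID value. Footnote c gives no clock time for the discharge-day procedures, so a site could grade the subject as 7 or 8 on leaving. A Day 5 or 6 discharge already lies within 2 days of Day 7, which may be why no call was scheduled. Programming specifications are kept in a separate document (SAP section 7). All of this stands, and it is why the range must include zero.

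It does not close the gap. If the discharge-day grade is not used, the value is missing. If the section 3.4.1 missing-data approach carries over to the other CMH endpoints, multiple imputation would then be applied to a subject whose discharge is known, and the sensitivity analysis would count that subject as a non-responder. If sites grade discharge day as 7 or 8, no text tells them to, so practice may differ between sites. On footnotes c and n, the specific instruction in c can be read as controlling, so the conflict is minor, but the wording should agree.

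A reader might infer more than the documents support:

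- **Early stopping of study drug.** Appendix A says "staff should make every effort to complete the full panel of assessments scheduled for the Day 7 visit", but neither it nor Protocol section 4.5 says on which day, or that the panel replaces the actual Day 7 record. These subjects stay in follow-up. The timing is unclear, and misdating cannot be claimed.
- **Loss of the fastest recoverers.** Subjects discharged on Days 1–4 do get a Day 7 call. Their problem is two records without a rule.
- **A Day 28 defect.** None is shown: discharged subjects have a Day 28 call.
- **A reversed treatment effect.** The documents state no effect size or discharge rate, so a change of sign cannot be supported.

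**Conclusion.** The concern holds for the Day 7 NIAID endpoints in subjects discharged on Days 5–6. That these subjects have no scheduled status between discharge and Day 14 follows directly from the schedule. That the discharge-day grade will be analysed as Day 7, and that it will be an inpatient grade, are strong inferences from the nominal-visit rule and the pre-dose timing of assessments. They are not stated rules.

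The size is unknown. It is zero if sites grade the discharge day as 7 or 8. On the assumed rates it is about 4.5–11 points of undercounted improvement if only baseline grade 5 is affected, and up to about 18 points if half of baseline grade 4 is too. The treatment difference is attenuated mainly if the drug speeds discharge. Two Day 7 outputs are affected, one of them descriptive. The SAP designates no primary efficacy endpoint, and mortality, respiratory failure and Day 28 endpoints are not touched by this mechanism. The change is worth making because it is nearly free and removes a known source of misclassification.

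**What to change.** - **SAP section 3.1.3 or 3.4.1.** Derive Day 7 NIAID status from actual study day and from discharge and readmission dates. A subject discharged alive before Day 7 and not readmitted by Day 7 is scored as not hospitalized, grade 7 or above. That alone settles the improvement endpoint for baseline grades 3 to 5. Where a Day 7 call exists, it takes precedence over the discharge-day record and decides between 7 and 8.
- **Protocol Appendix A, footnotes c and n.** Extend the existing Day 7 (±2 days) call, made after discharge, to every subject discharged before Day 7, and reword footnote n so that it allows this call. State the timing of the panel for subjects who stop study drug early, so that it is not left open.

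The cost is a few lines of derivation and one extra telephone call per Day 5–6 discharge. Discharge and readmission dates are already needed for length of hospitalization (Protocol section 7.1).

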APPENDIX B: CLINICAL LABORATORY ANALYTES

Standard Safety Chemistry Panel

Alanine aminotransferase	Albumin
Alkaline phosphatase	Aspartate aminotransferase
Blood urea nitrogen	Calcium
Carbon dioxide	Chloride
Creatine kinase	Creatinine
Estimated glomerular filtration rate	Gamma glutamyltransferase
Glucose	Lactate dehydrogenase
Potassium	Sodium
Total bilirubin	Total protein

Additional Chemistry Parameters

Arterial blood gas [1]

- Only if clinically indicated.

Coagulation

International normalized ratio

Partial thromboplastin time

Prothrombin time

Endocrinology

Beta human chorionic gonadotropin [1]

- Urine pregnancy tests will be performed for females of childbearing potential only.

Hematology

Hematocrit

Hemoglobin

Platelets

Red blood cells

White blood cell count and differential [1]

- Manual microscopic review is performed only if white blood cell count and/or differential values are out of reference range.

Biomarkers/Pharmacodynamic Parameters

Angiopoietin-2

C-reactive protein

D-dimer

High mobility group box 1

Interleukin-6

Interleukin-8

Tumor necrosis factor alpha

Additional Tests

Severe acute respiratory syndrome
coronavirus 2 [1]

1. Tests performed using polymerase chain reaction or other commercial or public health assay in any specimen.
